12.8 COVID-19/SARS-CoV-2 Test

The frequency and proportion of participants having negative or positive COVID-19/SARS-CoV-2 test will be summarized by treatment group at Days 7 and 15. For computing proportions, the denominator is the number of participants in the Safety population for the given treatment group and visit.

12.9 Drug Susceptibilities and MIC of TBA-7371

Drug susceptibility testing for isoniazid and rifampicin and MICs of TBA-7371 will be performed at Screening and Day 14. The frequency and proportion of participants having isoniazid resistance and/or rifampicin resistance detected by line probe assay will be provided by treatment group at Screening and Day 14. Any participant found to have isoniazid or rifampicin resistance by line probe assay will have further resistance testing performed and descriptive summaries of those results will be compiled. For computing proportions, the denominator is the number of participants in the Safety population for the given treatment group and visit.

MIC of TBA-7371 will be summarized by treatment group using descriptive statistics at Screening and Day 14.

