a. **Early Withdrawal Visit (EWV) or Unscheduled Visit.** Participants who withdraw before Day 14 will be asked to complete the EWV assessments within 2 Days of withdrawal. Participants who complete the Study Treatment Phase, but do not return for the Day 28 visit will be asked to return for the Day 42 visit. If access to sites is limited due to the local status of the COVID-19 pandemic, the Day 28 and Day 42 visits could potentially be conducted by telephone. Procedures and assessments conducted during an unscheduled visit will be at the discretion of the investigator in consultation with the medical monitor.

2. Introduction

TBA-7371 is a non-covalent inhibitor of mycobacterium tuberculosis (Mtb) deca-prenylphosphoryl- β -D-ribose 2'-epimerase 1 (DprE1), an enzyme involved in mycobacterial cell wall synthesis. TBA-7371 demonstrates potent bactericidal anti-Mtb activity in vitro, with a minimum bactericidal concentration (MBC) similar to its minimum inhibitory concentration (MIC) against replicating Mtb. It has a narrow spectrum, with activity limited to mycobacteria. Like other cell-wall biosynthesis inhibitors, TBA-7371 is not active against low-oxygen induced non-replicating bacteria. TBA-7371 was highly active against a panel of 96 clinical Mtb isolates representative of global phylogeny and geographical origin, and with differing drug-susceptibility profiles, including extensively drug-resistant TB (XDR-TB). The MIC₉₀ of TBA-7371, i.e. the MIC for at least 90% of isolates of this panel, is 0.64 μ g/mL and the MIC range is 0.04-5.12 μ g/mL, where the distribution of MICs is unrelated to the drug-susceptibility or genotype of the strain, suggesting utility globally, and against drug-sensitive and drug-resistant TB. Activity against drug-resistant Mtb isolates is expected for TBA-7371 because its drug target, DprE1, is novel, compared to those of currently used TB drugs. Mtb mutants resistant to TBA-7371 are selected at a frequency of $4-7 \times 10^{-7}$, similar to the reported *in vitro* resistance frequency for clinically relevant anti-TB agents like ethambutol.

No active metabolites of TBA-7371 have been identified thus far.

More information on the PK and pharmacodynamics (PD) of TBA-7371 is provided in the Investigator Brochure.

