8.2. Bactericidal Activity Assessment

8.2.1. Overnight Sputum for EBA assessment and Exploratory Measurements

Overnight sputum will be collected from 3 PM to 7 AM of the following morning.

The overnight sputum samples collected on Day -2 and Day -1 of the Screening Phase will be used to determine baseline EBA. Subsequent overnight sputum samples will be collected every day/night (Day 1 to Day 14) to assess changes in bacterial burden during the Study Treatment Phase.

Early bactericidal activity will be assessed on each sputum sample by 3 different methods: 1) CFU on solid media culture (primary), 2) time to sputum culture positivity (TTP) in MGIT culture, 3) LAM assay. Confirmation of Mtb will be performed on solid media and MGIT cultures as necessary using available commercial methods.

A commercial molecular test to assess isoniazid and rifampicin sensitivity, GenoType MTBDRplus (HAIN Lifesciences), will be utilized on positive MTB cultures from Day -2 (or, if Day -2 unavailable, Day -1) and Day 14 to assess the drug susceptibilities at each visit. In addition, MICs of TBA-7371 will be batch tested on positive MTB cultures from Day -2 (or, if Day -2 unavailable, Day -1) and Day 14.

Extra samples from overnight sputum collections, as well as MTB isolates from cultures, will be stored for potential assessment of exploratory endpoints (see Section 8.10).

Details on sputum collection, handling and testing procedures, and on the laboratory are provided in the laboratory study instruction document.

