7 STUDY POPULATIONS

7.1 Populations for Analyses

Analysis populations are show in Table 6.

Table 6. Populations for Analyses

Population	Description
Randomized population	All participants randomly assigned to study intervention, who either have randomized date or randomization number.
Modified intention to treat (mITT) efficacy population	All participants randomly assigned to study intervention, who received at least one dose of the study intervention. Participants will be analyzed according to the intervention they actually received.
Per Protocol (PP) efficacy population	All participants randomly assigned to study intervention, who received the study intervention, and did not substantially deviate from the protocol procedures. Participants who substantially deviated will be identified prior to database lock. Participants will be analyzed according to the intervention they actually received.
Safety population	All participants randomly assigned to study intervention and who received at least one dose of the study intervention. Participants will be analyzed according to the intervention they actually received.
PK population	All participants who received at least one dose of TBA-7371 and have at least one pair of pre- and post-dose blood samples with measurable concentrations.

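### SAP 12.9 reads as counting untested participants as not resistant to isoniazid/rifampicin, and separately summarises TBA-7371 MIC by visit with no within-participant change

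*SAP*

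**What the plan says.** **Resistance to isoniazid and rifampicin.** SAP 12.9 plans counts and percentages, worded in part as "participants having isoniazid resistance and/or rifampicin resistance detected by line probe assay will be provided by treatment group at Screening and Day 14". For that proportion, "the denominator is the number of participants in the Safety population for the given treatment group and visit". SAP 7.1 defines the Safety population as "All participants randomly assigned to study intervention and who received at least one dose of the study intervention", with no condition on having a culture or assay result. Under Protocol 8.2.1 the line-probe test "will be utilized on positive MTB cultures from Day -2 (or, if Day -2 unavailable, Day -1) and Day 14".

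**TBA-7371 MIC.** SAP 12.9 says only that "MIC of TBA-7371 will be summarized by treatment group using descriptive statistics at Screening and Day 14". Protocol 8.2.1 again limits testing to cultures that grew: "MICs of TBA-7371 will be batch tested on positive MTB cultures from Day -2 (or, if Day -2 unavailable, Day -1) and Day 14". SAP 12.9 names no change from Screening, fold-rise category or shift table for either test.

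**Elsewhere in the SAP.** Section 12.7 gives changes from baseline, allows a fold-change scale, provides baseline-to-visit shift tables, and restricts denominators to participants with non-missing values. The by-time-point summaries in 12.2 to 12.6 likewise use participants assessed, or with non-missing values, at that time point. Section 9.1 lists every measured variable by participant and includes the minimum and maximum in summaries of continuous variables.

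**The concern.** A participant whose Day 14 culture did not grow, was contaminated, or was never collected has no line-probe result. If that participant stays in the denominator, the absence of a result is treated as a finding of no resistance, and the reported proportion can only be too low.

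The MIC question is different. Screening and Day 14 are summarised as two separate group descriptions. Participants without a Day 14 isolate drop out of the second, so the two may not cover quite the same people. Even when they do, a rise in one participant's own isolate is compared with the spread between isolates instead of with that participant's own starting value.

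The unpaired layout also affects the line-probe results. The same proportion at both visits could be one participant resistant throughout, or one participant resistant at Screening and another newly resistant at Day 14.

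At stake is how clearly the report shows resistance present at entry and any change in susceptibility during treatment. No efficacy or safety test is affected.

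**Working it through.** SAP 12.9 states no figure, so there is none to reproduce for this output.

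**Inputs**
- Group size: 15 per TBA-7371 regimen and 15 HRZE pooled (SAP 6.1).
- Withdrawals: the first two drop-outs per cohort are not replaced, and at least 16 of 18 complete treatment (SAP 6.1).
- MIC range: 0.04 to 5.12 µg/mL in a panel of 96 clinical isolates (Protocol 2). 5.12/0.04 = 128 = 2^7, or seven doubling dilutions.
- Number with a valid Day 14 result, m: not given in the documents. Assumed values are 13, 12 and 10. The value 13 arises if both unreplaced withdrawals in a cohort fall in the TBA-7371 arm (15 − 2).

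**1. Denominator.** With one resistant isolate, the literal rule gives 1/15 = 6.7%. Among those tested it is 1/m:
- m = 13: 7.7%
- m = 12: 8.3%
- m = 10: 10.0%

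The reported figure is m/15 of the proportion among those tested, so it is too low by 13% in relative terms at m = 13 and by 33% at m = 10.

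**2. How many are likely to be tested.** SAP 11.1.1 suggests a starting intercept of 6 log10 CFU/mL. The largest reference decline in SAP 6.2 is 0.122 log10 per day: 14 × 0.122 = 1.7, leaving about 4.3 log10. Protocol 9.2 gives 0.112 for the same reference: 14 × 0.112 = 1.6, leaving about 4.4. These are a model starting value and another study's means, not forecasts for this trial. They do suggest that most cultures would still grow at Day 14.

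**3. Effect of one MIC rise on group summaries.** If one of m values rises f-fold and the others stay put, the geometric mean changes by f^(1/m). For m = 15:
- f = 4: 1.10-fold
- f = 8: 1.15-fold
- f = 16: 1.20-fold

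For m = 10 the changes are 1.15-, 1.23- and 1.32-fold. If all 15 start at the same value, the arithmetic mean changes by (14 + f)/15, that is 1.2-, 1.47- and 2.0-fold. Even the 16-fold case therefore moves it by one doubling dilution. With one value changed, the median can move at most to the neighbouring ordered value.

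**4. Median and maximum when isolates differ.** A simulation of 15 participants assumed a between-isolate SD of 0.75 to 1.5 dilutions, assay noise of at most one dilution, and one participant with a true rise. Across these settings:
- The median did not rise in 80 to 92% of runs.
- The maximum rose by two or more dilutions in 12 to 20% of runs for a 4-fold rise, 28 to 62% for 8-fold and 49 to 91% for 16-fold.
- A paired count of rises of 4-fold or more picks up the case by construction.

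**5. Why the number tested should be shown.** The chance of seeing at least one case at a true 10% rate is 1 − 0.9^m. At m = 15 this is 79.4%, matching the roughly 80% that SAP 6.2 gives for adverse events. At m = 10 it is 65.1%. A zero count cannot be interpreted without m.

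**The case against.** Several points on the other side stand.

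- **The denominator wording is not airtight.** Its closing reference to the visit could be meant to restrict the count to participants with data at that visit. SAP 12.8 uses the same phrase. Counts appear beside proportions, and any line-probe resistance leads to further testing with its own summaries.
- **A reader might infer that this denominator dilutes resistance arising on TBA-7371 monotherapy.** It does not. The rule covers isoniazid and rifampicin only, and those drugs are given only in the four-drug HRZE arm. Resistance to TBA-7371 would show in the MIC, which has no such denominator.
- **A reader might infer that a rising MIC appears in no table.** SAP 9.1 prints the minimum and maximum and lists individual values. If 14 participants are at 0.32 and one goes from 0.32 to 5.12, the maximum moves with it. It may not move when another participant already has a high value at Screening.
- **A reader might suppose that only a third of participants would be tested at Day 14**, so that 1/15 = 6.7% stands against 1/5 = 20%. Step 2 of the working makes that unlikely.
- **A reader might take detecting emergent resistance to be the stated purpose of the Day 14 MIC.** The documents do not say so. Susceptibility testing and emergence of resistance are named as possible exploratory objectives, with details left to separate plans. The 128-fold range comes from a global panel that includes extensively drug-resistant strains, so it need not be the spread in this trial.

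What remains is that SAP 12.9 itself collects paired results, reports them unpaired, and gives a denominator that does not match who is tested.

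**Conclusion.** The point holds as two separate and modest defects in a descriptive output.

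The isoniazid/rifampicin proportion is biased low on the literal reading. The size depends on the number tested, which is an assumption: 6.7% against 7.7% for 13 of 15, or 10% for 10 of 15. If the sponsor meant participants with results, the text should say so, as other SAP sections do.

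The unpaired MIC summary largely hides a rise in a single participant: 1.10- to 1.20-fold in the geometric mean for a 4- to 16-fold rise among 15, with the median usually unchanged. The maximum shows some cases and the listings show all of them, but without a prespecified definition or count. The geometric-mean result is arithmetic and assumes only that the other participants' values are unchanged. The simulation percentages rest on assumed spread and assay noise.

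The documents do not support a claim that TBA-7371 resistance is diluted by the denominator or absent from all outputs.

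**What to change.** In SAP 12.9:

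1. Define the resistance denominator as participants with a valid line-probe result at that visit, and report the number not tested, with reasons.
2. For participants with MIC results at both visits, tabulate the within-participant Day 14/Screening ratio on the log2 scale by treatment group, with a count above a fold-rise threshold that the sponsor fixes before seeing the results. Keep the by-visit summaries.
3. Cross-tabulate paired Screening and Day 14 line-probe results, so that resistance present at entry is separated from resistance first seen at Day 14.

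The data are already being collected, so the cost is SAP wording and about one extra table. Paired numbers will be smaller than group sizes, so each table should show its n.

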13 PHARMACOKINETIC ANALYSES

All PK and PK/PD analyses will be performed for the PK population.

13.1 TBA-7371 Pharmacokinetics

Timing of TBA-7371 sampling for participants randomized to TBA-7371 will be as follows:

	QD Dosing	BID Dosing	TID Dosing
Screening Phase	Predose	Predose	Predose
Study Treatment Phase	
 Predose on Days 1, 2, 4, 7, and 14. 30 min, 1h, 2.5h, 3h, 4h, 6h, 7h, 10.5h, 12h, and 16.5h on days 1, 7, and 14. 	
 Predose on Days 1, 2, 4, 7, and 14. 30 min, 1h, 2.5h, 3h, 4h, 6h, 7h, 10.5h, and 12h on days 1, 7, and 14. 	
 Predose on Days 1, 2, 4, 7, and 14. 30 min, 1h, 2.5h, 3h, 4h, 6h, and 7h on days 1, 7, and 14.

TBA-7371 concentrations below the limit of quantitation will be set to 0. TBA-7371 concentrations will be summarized by treatment group using nominal time points for all participants in the PK population. The following descriptive statistics will be provided: N, arithmetic mean, standard deviation, arithmetic percent coefficient of variation (CV), median, minimum, maximum, geometric mean, and geometric percent CV. Linear and semi-log plots of individual and mean concentrations versus nominal time will be presented by treatment group. Plasma concentration of TBA-7371 having value 0 will be excluded from semi-log plots.

The following PK parameters of Days 1, 7, and 14 will be derived using non-compartmental model.

Day 1	Day 7	Day 14
C _{max} , T _{max} , C _{last} , T _{last} , AUC _{inf} , AUC _{last} , AUC _{tau} , C _{min} , half-life,	C _{max} , T _{max} , C _{last} , T _{last} , AUC _{inf} , AUC _{last} , AUC _{tau} , C _{min} , half-life, accumulation ratio (C _{max} of day 1/C _{max} of day 7)	C _{max} , T _{max} , C _{last} , T _{last} , AUC _{inf} , AUC _{last} , AUC _{tau} , C _{min} , half-life, accumulation ratio (C _{max} of day 1/C _{max} of day 14)

- C_{max} – maximum plasma concentration
- C_{min} – minimum plasma concentration
- T_{max} – time to maximum plasma concentration
- λ_z – elimination rate constant. The elimination rate constant will be calculated as the negative of the slope of the terminal log-linear segment of the plasma concentration-time curve. The slope will be determined from a plot of the natural log of the terminal plasma concentrations against time; at least 3 terminal plasma concentration time points, beginning with the final concentration \geq LLOQ and not including C_{max}, will be selected for the determination of λ_z; the regression will have a coefficient of determination R² \geq 0.9000.
- Half-life – terminal half-life = ln(2) / λ_z.

- AUC_{last} – area under the plasma concentration-time curve from 0 up to the last measurable concentration \geq LLOQ. AUC is calculated using the linear trapezoidal method.
- AUC_{inf} – AUC extrapolated to infinity. $AUC_{inf} = AUC_{last} + C_{last} / \lambda_z$, where C_{last} is the last measurable concentration \geq LLOQ and λ_z is the terminal phase rate constant.
- AUC_{tau} – AUC to the end of the dosing period.

PK parameters of days 1, 4, 7, and 14 will be summarized using descriptive statistics number of participants, arithmetic mean, standard deviation, arithmetic percent CV, median, minimum, maximum, geometric mean, and geometric percent CV and will be provided by treatment group.

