12. **Overnight sputum collection for EBA assessment and exploratory measurements.** Overnight sputum will be collected from 3 PM to 7 AM of the following Day (16 hours) on Days -2 and -1 during Screening Phase and on 14 consecutive Days during the Study Treatment Phase (Days 1 to 14) for EBA assessment. The last collection will finish at 7 AM of Day 15. Drug susceptibility testing for isoniazid and rifampicin, and minimum inhibitory concentrations (MIC) of TBA-7371 will be performed on either of Day -2 or Day -1, and again on Day 14. Aliquots from each sample, as well as MTB isolates from cultures, will be stored and may be used for exploratory measurements.
13. **Spot sputum collection for exploratory measurements.** The participant should spontaneously produce (i.e., not induced) a spot sputum specimen for collection into RNA preservation media. If specimen cannot be collected due to participant inability to produce sputum, or due to operational limitations with RNA media collection kits, it is not considered a protocol deviation.
14. **Recording of AE, SAE (including serious ADR) and AESI; recording of concomitant treatments.** Adverse events (AE), serious adverse events (SAE), including serious adverse drug reactions (ADR), adverse events of special interest (AESI) and concomitant treatments will be recorded from the time each participant has signed the informed consent form (ICF) until he/she has completed the last follow- up visit (Day 42) or the Early Withdrawal Visit (EWV).
15. **Blood/serum sample collection for PK measurements.** WILL BE CONDUCTED ONLY IN PARTICIPANTS RANDOMIZED TO TBA-7371.
Timing of sampling will be as follows:
 - Study Treatment Phase: Days 1, 2, 4, 7 and 14 before administration of the 1st daily dose of study drug; in addition, on Days 1, 7 and 14 samples will also collected 30 min (+/- 5 min) and at 1h, 2.5h, 3h, 4h, 6h, 7h, 10.5h, 12h, 16.5h (+/- 15 min) after 1st daily dose of study drug. (see Table 4). Patients assigned to BID dosing will not have collections at 16.5h, and the 12h sample will be taken prior to the second daily dose. Patients assigned to TID dosing will not have collections at 10.5h, 12h and 16.5h, and the 7h sample will be taken prior to the second daily dose.When timing coincides, samples must always be taken after recording of ECG and vital signs.
16. [REDACTED]

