See Section 10.6 (Appendix 6) for a list of commonly used prohibited medications (based on exclusion criteria # 11 to # 16). Please note that the list is not comprehensive and other medications with the features described below are also prohibited.

11. Use of medications active against Mtb within 3 months prior to the first dose of study drug.
12. Use of systemic immunosuppressive medications within 14 days prior to the first dose of study drug.
13. Use of strong inhibitors or strong inducers of cytochrome P450 (CYP) enzymes within 14 days prior to the first dose of study drug.
14. Use of inhibitors of phosphodiesterase (PDE) enzymes within 14 days prior to the first dose of study drug.
15. Use of medications known to affect the eye within 3 months prior to the first dose of study drug.
16. For HIV+ patients, use of medications listed in Section 10.6 (Appendix 6) within 3 months prior to the first dose of study drug.

Prior/Concurrent Clinical Study Experience

17. Participation in other clinical study(-ies) with investigational agent(s) within 6 months prior to trial start.

Diagnostic Assessments

18. The following laboratory values from blood collected during the Screening Phase, which represent Grade 2 or higher abnormalities per DAIDS Toxicity Table Version 2.1 (see Section 10.4, Appendix 4), will be cause for exclusion:
 - AST, ALT, alkaline phosphatase (ALP) \geq 2.5x upper limit of normal (ULN)

- Total bilirubin \geq 1.6x ULN
- Creatinine \geq 1.3x ULN
- Hemoglobin < 10 g/dL (male) or 9.5 g/dL (female)
- White Blood Cell Count (WBC) < 2,000 / mm³
- Platelets \leq 100,000 /mm³
- INR \geq 1.5x ULN
- PTT \geq 1.66 ULN
- PT \geq 1.25x ULN

ULN= upper limit of normal for local laboratory values

Grade 2 or higher abnormalities in other laboratory parameters from blood or urine Grade 1 abnormalities, or abnormalities from laboratory parameters not included in the DAIDS Toxicity Table Version 2.1, may lead to exclusion if the investigator considers them clinically significant.

Other Exclusion Criteria

19. History of allergy or hypersensitivity to any of the study drugs or related substances.
20. Positive urine drug screening for cocaine AND/OR amphetamines AND/OR opiates AND/OR methamphetamines. Note: screening will also be conducted for cannabinoids and results documented in the CRF; however, a positive test for cannabinoids is not an exclusion criterion.

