9.2 Definitions

Screening EBA Measure: Average of the EBA measurements (i.e., log CFU, TTP in MGIT, and log concentration of sputum LAM) from the day -2 and day -1 overnight sputum samples of the screening phase will be used to determine the screening EBA measurement. If one of the overnight sputum samples is missing, the single non-missing sample will be directly used as the screening EBA measurement.

Baseline definition for other efficacy and safety variables: The last assessment made prior to the first administered dose of study intervention will be considered baseline for analysis purposes. Baseline values of ECG and vital signs are measured on Day 1 before the first dose of study medication is administered.

Day 1: Study day 1 is the day of first administration of TBA-7371 or HRZE. Positive study days will be counted forward from Day 1. Day -1 will be the date immediately preceding Day 1, and negative study days will be counted backward from Day 1.

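### SAP 13.1 makes Day 1 Cmin zero by construction; the sample behind Cmin and the handling of zeros need to be stated

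*SAP*

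**What the plan says.** SAP 13.1 schedules samples "Predose on Days 1, 2, 4, 7, and 14" for the QD, BID and TID regimens alike. Protocol Section 1.3 places these "Days 1, 2, 4, 7 and 14 before administration of the 1st daily dose of study drug". On Days 1, 7 and 14 further samples follow the first dose, up to 16.5 h for QD, 12 h for BID and 7 h for TID.

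The data rule is that "TBA-7371 concentrations below the limit of quantitation will be set to 0". Zeros are then left out of semi-log plots, and that is the only provision made for them.

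On parameters, SAP 13.1 says "The following PK parameters of Days 1, 7, and 14 will be derived using non-compartmental model". Cmin is in the Day 1 column and is defined only as the "minimum plasma concentration". No interval is given, and the sample before the first dose is not excluded. The protocol's abbreviation list is no more specific. At the end of 13.1, "PK parameters of days 1, 4, 7, and 14 will be summarized using descriptive statistics", among them the geometric mean and geometric percent CV. Protocol Table 9 asks for the same statistics.

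Cmin is a named secondary PK endpoint in protocol Section 3.2 and SAP Section 6.5.

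**The concern.** Each rule is ordinary on its own. Together they fix the answer for Day 1 before any data are seen: the lowest value in the profile is the one taken before the drug was given, and it has been set to 0. A named endpoint would then be reported for Day 1 as a row of zeros in every regimen, with geometric statistics that software will return as missing or as zero.

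The likely practical result is that the programmer departs from the text. One may take the lowest post-dose value, which can be an absorption-phase sample rather than a trough. Another may take the last sample, and a third may follow the text and report zero. The same endpoint could then carry different numbers, with nothing in the SAP to say which is correct.

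A smaller mismatch sits beside it. Parameters are derived for Days 1, 7 and 14, but the summary sentence adds Day 4. Day 4 has a single pre-dose sample, so it has no Cmax, Tmax, AUC or half-life to summarise.

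**Working it through.** The plan gives no figure for Cmin, so there is nothing to reproduce first. The check applies the written rules in order.

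**1. Day 1 pre-dose concentration.** SAP 9.2 says "Study day 1 is the day of first administration of TBA-7371 or HRZE", so the Day 1 pre-dose sample precedes all study drug. Protocol Section 5.2 excludes "Participation in other clinical study(-ies) with investigational agent(s) within 6 months prior to trial start", so carry-over is not expected. The value is below quantitation and is set to 0.

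**2. Day 1 Cmin.** Concentrations cannot be negative, so Cmin = min(0, post-dose values) = 0. This needs no assumption about half-life or assay limit.

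**3. Summary statistics when every x = 0.**
- Geometric mean = exp(mean of ln x): ln 0 is undefined.
- Geometric CV = 100·√(exp(var of ln x) − 1): undefined.
- Arithmetic CV = 100·SD/mean = 100·0/0: undefined.
- The nth-root-of-product form of the geometric mean returns 0, which is equally uninformative.

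**4. Does dropping the Day 1 pre-dose sample settle it?** The documents give neither a half-life nor an assay limit (LLOQ), so this part is illustrative only. A one-compartment oral model was simulated at the SAP sampling times, with 15 participants per regimen. Assumed half-lives were 2, 4 and 8 h, and assumed LLOQs were 0.001 and 0.01 of dose/volume, which gives 3 × 2 × 3 = 18 scenarios. The table counts participants out of 15 with Cmin = 0.

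| Half-life, LLOQ, regimen | Day 1, all samples | Day 1, pre-dose left out | Day 7 | Day 14 |
|---|---|---|---|---|
| 2 h, 0.001, QD | 15 | 2 | 10 | 10 |
| 2 h, 0.01, QD | 15 | 11 | 15 | 15 |
| 2 h, 0.01, BID | 15 | 6 | 6 | 6 |
| 4 h, 0.001, QD | 15 | 0 | 1 | 1 |
| 4 h, 0.01, QD | 15 | 0 | 3 | 3 |
| other 13 scenarios | 15 | 0 | 0 | 0 |

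Day 1 Cmin is 0 for 15/15 in all 18 scenarios. Leaving out the pre-dose sample removes the automatic zero, but some zeros can remain if the half-life is short. For QD, the third column ends at 16.5 h. A Day 2 pre-dose value at 24 h would show at least as many zeros as Day 7, because the Day 7 pre-dose sample follows more doses. A rule for zeros is therefore needed as well as a definition of Cmin.

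**5. Which samples close a dosing interval?**
- Day 1: Day 2 pre-dose for QD, 12 h for BID and 7 h for TID. All three are already scheduled.
- Day 7, QD: the interval ends at Day 8 pre-dose, which is not sampled.
- Day 14, QD: the interval ends on Day 15. A Day 15 draw appears only in protocol Section 8.7, not in the SAP 13.1 table or in footnote 15 of the schedule of activities.
- TID: doses at 0, 7 and 14 h leave gaps of 7, 7 and 24 − 14 = 10 h, so the 7 h sample closes a shorter interval than the overnight one.

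**The case against.** The strongest reply is that little is lost. SAP 13.1 summarises concentrations at every nominal time, so the Day 2, 4, 7 and 14 pre-dose values, the 12 h BID value and the 7 h TID value are all tabulated and plotted. They are simply not labelled Cmin. This stands, and a reader who inferred that the troughs go unused would be wrong.

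Nor do the documents support the inference that a Day 1 to Day 14 trough comparison is spoiled. None is planned. The only cross-day parameter is the accumulation ratio, which uses Cmax. The correlations in SAP 13.2 use AUCinf, Cmax and T>MIC, and the Emax model in SAP 13.3 uses Day 14 Cmax.

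SAP 9.1 also offers the geometric mean and coefficient of variation only if appropriate, so an all-zero row could be left blank. That is fair as a general convention, but 13.1 does not repeat the qualifier, and blanking the cells does not make the remaining zeros informative.

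A PK programmer may well drop the Day 1 pre-dose sample without being told. The SAP should still say so, since the written rule gives a different answer. The PK population definition does not help: it asks for a measurable pre- and post-dose pair on no particular day, which governs who is included rather than which samples enter Cmin.

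Finally, one end-of-interval definition for all three days looks tidy, but the schedule does not support it for QD on Day 7, nor reliably on Day 14.

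**Conclusion.** The point holds, and it is minor. As written, SAP 13.1 gives Day 1 Cmin = 0 for every PK-population participant with the Day 1 pre-dose sample, in all five regimens. That is at most about 75 participants as planned; the exact number depends on who enters the PK population and has the sample. The log-based geometric mean and geometric CV cannot be computed for that row. The result assumes that the pre-dose sample is drug-free and that it enters Cmin, which nothing in the SAP prevents.

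The harm is confined to one day of one descriptive secondary PK parameter. Cmax, AUC, the exposure-response model and the efficacy conclusions are unaffected. On Days 7 and 14 zeros are not automatic; whether any occur depends on a half-life and an assay limit that the documents do not give. The same gap in the handling of zeros affects the Day 1 pre-dose row of the concentration table. The Day 4 mention is a separate drafting inconsistency within 13.1.

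**What to change.** In SAP 13.1:

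1. For Day 1, exclude the sample before the first dose and take Cmin as the concentration at the end of the first dosing interval: Day 2 pre-dose for QD, 12 h for BID, 7 h for TID. Note that for TID this is a 7 h interval, whereas the pre-dose trough on later days follows a 10 h gap.
2. For Days 7 and 14, keep Cmin as the minimum over that day's samples, including that day's pre-dose trough.
3. State how zeros enter geometric statistics, for concentrations as well as parameters. For example, report the number of zeros and show the geometric statistics as not calculated when any are present.
4. Remove Day 4 from the parameter summary so that it agrees with derivation on Days 1, 7 and 14, and report Days 2 and 4 as pre-dose concentrations only.

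The cost is a few sentences and a small programming specification. No samples are added and trial conduct does not change.
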